#### **12.5.2.9 Exploratory Efficacy Analyses**

In an exploratory analysis, patients experiencing an immune response in all four treatment arms will be compared to those who did not experience an immune response. The analysis will include a univariate comparison of patient and clinical variables at baseline as well as a comparison of any difference between immune responders and non-responders for the following endpoints: proportion with progressive or recurrent disease at selected time points, disease-free survival, proportion undergoing post-treatment TURBT or fulguration or cystectomy, and overall survival.

In an additional exploratory analysis, the proportion of patients whose disease has recurred to a lower stage than at screening and the proportion of patients whose disease has recurred to the same extent as at screening will be compared between the experimental and control groups and presented as an OR with 95% CI.

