## **6.2 Phase 2**

**6.2.1 Phase 2 Schedule of Events**

Procedure	Screen	Baseline	Week 1 	Weeks 2-6 	Week 7	Weeks 8-12 	Week 13	Weeks 14-16 	Week 25	Weeks 26-27 	Week 28	Week 37	Week 49	Weeks 50-52 	Week 56 (EOT) 	Long-term Follow-up
Study Day	≤ -4 wks.	-3 to 1	1		43 (±1)		85 (±1)		169 (±3)		190 (±3)	253 (±3)	337 (±3)		386 (±3)	Q3mos. 2yrs; Q6mos. 3 rd yr
Baseline Documentation																
Informed Consent	X															
Verify All Eligibility Criteria	X															
Enrollment/Randomization		X														
Medical History	X 	X														
Physical Exam 	X	X 					X								X	
Pathology Review	X															
12-lead ECG	X														X	
Laboratory Studies																
Immunologic Response 		X			X 		X				X 				X	
Hematology, Chemistry and LDH, Dipstick Urinalysis	X 	X 					X		X			X	X		X	
Pregnancy Test (urine or serum)	X 	X 													X	
Autoimmune Labs 		X													X	
Tumor Assessments																
Cystoscopy/Cytology for disease recurrence per SOC 							X		X			X	X			X 
Tumor collection for antigen screen			X													
Dosing																
Study Product Administration 			X	X	X	X		X		X	X			X		
BCG Administration 			X	X				X		X	X			X		
Other Clinical Assessments																
Autoimmune Phenomena 		X					X								X	
Adverse Events 			X	X	X	X	X	X	X	X	X	X	X	X	X	
Concomitant Medications	X 	X	X	X	X	X	X	X	X	X	X	X	X	X	X	
Survival and subsequent therapy																X

 Screening evaluations should be completed ≤ 2 weeks of first dose.

 PE, hematology, chemistry, LDH, dipstick urinalysis and pregnancy test do not need to be repeated at Baseline if they were performed at Screening within three days prior to first dose.

 First dose of study product should occur within 6 weeks of baseline staging procedure.

 Weekly study evaluations should be completed within ±1 day of the target visit date.

 EOT evaluations should be completed 4 weeks ±3 days after last dose of study product or early discontinuation of study treatment.

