-  PE at screening and Week 56 (End of Treatment) will have a full examination of body systems and vital signs. Other PE evaluations will be limited to symptoms, weight and vital signs.
-  70mL of heparinized blood, 10mL of non-heparinized blood, and 24mL urine will be collected at the indicated visits.
-  ANA, TSH, ESR, C-reactive protein are required. Other tests (e.g. RF, T3, T4, thyroid antibodies) will be performed only as clinically indicated.
-  All patients will have a cystoscopy/cytology performed at Week 13. If clinically indicated, a repeat biopsy will be performed. Patients with evidence of disease at an assessment may continue on treatment if judged by the investigator to be in the patient's best interest (e.g. would normally receive another course of BCG therapy as SOC). Upon discontinuation of study treatment, additional treatment will be at the discretion of the treating physician, and patients will continue in long-term follow-up on the study.
-  For Arms 1-4: Patients will receive study product as the number of intradermal injections required to reach the number of cells per dose with no more than 0.1 mL per injection (approximately 4-6 injections). Patients should remain on site for 30 minutes following each vaccination for observation of adverse events.
-  For Arms 1-3 only.
-  Includes eye exam for dry eyes, lymph node and joint assessment and skin exam for vitiligo and rashes.
-  AEs should be recorded from first dose through four weeks following the last dose of study medication regardless of the causal relationship to the study medication. AEs considered related to study medication should be recorded at any time regardless of when they occurred.
-  Samples to be collected prior to dosing
-  Cystoscopy/Cytology for disease recurrence per SOC (approximately every 3 months for 2 years then every 6 months for up to a year). Patients who are determined to have evidence of disease will have SOC treatment per the discretion of the investigator and will continue in long-term follow-up on the study.
-  Weekly study evaluations should be completed within  $\pm 3$  days of the target visit date.

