#### **6.2.3.4 Phase 2 Assessments at Week 7 (Day 43 $\pm 1$ )**

The following procedures will be performed at this visit:

- Blood and urine collection for immune monitoring collected prior to dosing
- Study product administration
  - Weekly study product dosing

- Monitor patient on site for potential acute reactions for 30 minutes after study product administration
- Record adverse events
- Record concomitant medications

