#### **6.2.3.6 Phase 2 Assessments at Week 13 (Day 85±1)**

The following procedures will be performed at this visit:

- Physical exam (symptoms, weight and vital signs only)
- Blood and urine collection for immune monitoring
- Hematology, chemistry with LDH, and dipstick urinalysis
- Cystoscopy/Cytology and, if indicated, a repeat biopsy – per SOC to evaluate for evidence of disease. *Note: Patients with evidence of disease may continue on treatment if judged by the investigator to be in the patient's best interest. Patients who discontinue study treatment will continue in long-term follow-up. If biopsy was performed, provide at least 4, non-stained, 10 micron sections for TCR sequencing and analysis of infiltrating T-cells. If slides are not available, FFPE tissue (≥50 microns) is also acceptable.*
- Autoimmune Phenomena – Assessment of adult autoimmune system disorders (including: eye exam for dry eyes, lymph node and joints assessment for swelling, and skin exam for vitiligo and rash)
- Record adverse events
- Record concomitant medications

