The frequency of IFN $\gamma$  producing CD8+ cells is thought to mirror the frequency of cytotoxic CD8+ cells. However, cytotoxicity is primarily mediated by perforin and granzymes following granule exocytosis. In some instances IFN $\gamma$  secretion and granule exocytosis are uncoupled. Therefore, the direct measurement of grzB secretion by ICS may provide a more direct readout for antigen-specific granule exocytosis and cytotoxicity. For clinical efficiency it may be important to detect both IFN $\gamma$  secretion and grzB exocytosis. Antigen specificity of the ICS response will be evaluable by comparing responses generated using the various stimulator cell populations and specific shared bladder cancer antigens as indicated. This will also enable separation of the ‘allo-antigen’ specific response with the potential parent cell line tumor-antigen-specific response. Positive responses will be defined as a greater than two-fold increase in the number of IFN $\gamma$  positive CD8+ T cells compared to baseline.

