5.3 Covariates and Subgroups

There will be no covariate or subgroup analysis in the phase 1 component of this protocol.

For the phase 2 component of the study, the following subgroups may be used to further summarize and evaluate the efficacy endpoints, if sufficient data are available:

- Risk of recurrence (High risk vs intermediate risk)
- Carcinoma in situ (yes vs no)
- Patient immune response
- TNM stage, grade, and severity
- BCG naïve or BCG recurrent; number of prior BCG treatments
- Screening TURBT characteristics (Re-resection TURBT at screening, muscle in specimen)
- Number of prior TURBTs
- Number and size of tumors
- TIL status
- Demographics
- Academic vs. Community practices
- Use of Blue Light cystoscopy
- Use of peri-operative chemotherapy

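### The exploratory responder comparison fixes no time for classing response and pools all four arms, so it is open to immortal-time bias and to confounding by treatment

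*Protocol*

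**What the plan says.** Protocol 12.5.2.9, repeated in the synopsis, states that "patients experiencing an immune response in all four treatment arms will be compared to those who did not experience an immune response". The outcomes listed are recurrence or progression at selected times, DFS, repeat TURBT, fulguration or cystectomy, and OS.

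Protocol 10.2.1 gives the criterion: "Positive responses will be defined as a greater than two-fold increase in the number of" interferon-gamma-positive CD8+ T cells relative to baseline. It names no deciding visit and does not say whether the best, last or any sample counts.

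In Phase 2 the post-baseline samples fall at four points:
- Week 7 (Protocol 6.2.3.4): "Blood and urine collection for immune monitoring collected prior to dosing".
- Week 13 (6.2.3.6): "Blood and urine collection for immune monitoring". This visit also has the first scheduled disease assessment (6.2.1): "All patients will have a cystoscopy/cytology performed at Week 13".
- Week 28 (6.2.3.10), after the Week 13 and Week 25 disease assessments.
- Week 56 or early end of treatment (6.2.3.14), timed by 6.2.1: "EOT evaluations should be completed 4 weeks ±3 days after last dose of study product or early discontinuation of study treatment".

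Protocol 7.2.1 ends study treatment at progression and lets it either stop or continue at recurrence. Long-term follow-up (6.3) lists no immune blood draws.

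DFS and OS run from randomisation or treatment assignment (Protocol 12.5.2.3 and 12.5.2.5; SAP 3.5 and 7.2). CIS patients are an exception for overall DFS (Protocol 10.1 and 12.5.2.4). Persistent CIS, judged at 6 months, is dated back to randomisation. CIS patients who clear start their clock at the first disease-free date.

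SAP 5.3 lists "Patient immune response" as an optional efficacy subgroup, with no timing rule. SAP 5.5 restricts p-values to the primary analysis. SAP 7.3 leaves immune summaries and exploratory analyses, if applicable, to a separate plan.

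**The concern.** Responder status is known only after randomisation, while the outcome clock generally starts at randomisation. The most natural reading of the comparison is response at any time. Under that reading, a patient who recurs and stops treatment has fewer samples and so fewer chances to qualify. Part of the event-free time of responders is then a condition of becoming a responder, not a result of it.

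The second problem is separate. The comparison puts together placebo, two vaccine doses and a non-randomised arm without BCG. If the vaccine both raises the response rate and improves DFS, response will track outcome across the pooled arms even if it carries no information within any of them.

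At stake is an exploratory estimate linking immune response to clinical outcome. The primary analysis is not affected.

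**Working it through.** **The plan's own figures.** The documents give no figure for the responder analysis. The rates borrowed below are the design rates of 60% and 90% one-year DFS (Protocol 12.6.2). As a check that they are read correctly: with 23 evaluable per arm and one-sided alpha 0.10, exact Fisher power is 80.8%, against the stated 80%.

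**Step 1: chances to be called a responder.** Suppose each sample is positive with probability q, independently, and is unrelated to disease. The chance of at least one positive in k samples is 1 − (1 − q)^k.
- Recurs at Week 13, stops, no later sample (k = 2): 1 − 0.8² = 36% at q = 0.2; 1 − 0.6² = 64% at q = 0.4.
- Same patient with the early end-of-treatment sample counted (k = 3): 1 − 0.8³ = 49%; 1 − 0.6³ = 78%.
- Stays on treatment to Week 56 (k = 4): 1 − 0.8⁴ = 59%; 1 − 0.6⁴ = 87%.

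The gap between these patients arises with no biological link.

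**Step 2: simulated DFS hazard ratio with no true association.** Taken from the protocol: samples at Weeks 7, 13, 28 and 56, and disease assessments at Weeks 13, 25, 37 and 49; about every 13 weeks thereafter. Assumed, because the documents are silent or give no single value: 12-month DFS of 60% or 80%; q of 0.2 or 0.4; 0% or 50% of patients giving the same result at every sample (0% only in the last three rows); and the share who stop sampling at the first event. Hazard ratios come from 200,000 patients per scenario. Rejection rates come from 2,000 trials of 100 patients with a two-sided 5% log-rank test.

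| Rule for response and sampling | Null hazard ratio | Rejection |
|---|---|---|
| Any response; all stop at first event; no early end-of-treatment sample | 0.62–0.88 | 6–44% |
| Any response; half stop; no early end-of-treatment sample | 0.77–0.94 | 5–20% |
| Any response; all stop; early end-of-treatment sample counted | 0.85–0.96 | 5–13% |
| Any response; nobody stops sampling | 0.99–1.01 | 5–6% |
| Week 7 sample only, clock from randomisation | 0.99–1.01 | 5–6% |
| Response by Week 13, clock from Week 13 landmark | 1.00–1.02 | 4.5–5.7% |

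In the most affected scenario by one-year DFS (12-month DFS 60%, q = 0.4, all stop, no early sample), one-year DFS is 67% in responders and 41% in non-responders. With 81% classed as responders, the average is 0.81 × 67% + 0.19 × 41% = 62%. This is the 62% seen in both groups under the Week 7 rule, so the split comes from classification alone.

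The simulation does not model the CIS dating rules. OS was not simulated, because the documents give no OS rate.

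**Step 3: pooling.** Take Arms 1–3 as 25 placebo patients at 60% and 50 vaccine patients at 90%, with no association between response and DFS within arm. Response rates are assumed.
- 10% on placebo, 60% on vaccine. Responders: (2.5 × 0.6 + 30 × 0.9) / 32.5 = 28.5 / 32.5 = 88%. Non-responders: (22.5 × 0.6 + 20 × 0.9) / 42.5 = 31.5 / 42.5 = 74%.
- 30% on placebo, 40% on vaccine. Responders: (7.5 × 0.6 + 20 × 0.9) / 27.5 = 22.5 / 27.5 = 82%. Non-responders: (17.5 × 0.6 + 30 × 0.9) / 47.5 = 37.5 / 47.5 = 79%.

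A landmark leaves this second distortion in place; only an analysis by arm removes it.

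**The case against.** A reader might infer that the bias is built in and that the analysis must show a benefit of response. The documents do not support that. The any-time rule is the natural reading but is not stated. If response were set at Week 7, no scheduled Phase 2 disease assessment would come before it, and the hazard ratio stays at about 1.0.

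Nor is a late responder guaranteed to have been event-free until the sample. Patients with recurrence may stay on treatment and keep giving samples, and early stoppers are due an end-of-treatment sample. Both shrink the bias, and if nobody stopped sampling it would vanish. That limit cannot be fully met, since progression ends treatment and follow-up has no immune draws, but the true stopping rate is unknown.

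Other parts of the defence also stand:
- The analysis is labelled exploratory. SAP 5.5 plans no p-value for it, so the rejection rates above only indicate the size of the bias.
- The separate immune plan was not available and may set the rule.
- Nothing says the result will be used to claim that immune response drives benefit. Protocol 10.2.4 itself notes that these assays have not been strongly predictive of clinical response.

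What the defence does not supply is a classification time, a landmark or an arm stratification. The SAP population with at least six weekly doses does not fill the gap: that condition can be met by about Week 6, well before the samples at Weeks 28 and 56.

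**Conclusion.** The point holds as a gap in specification that leaves the estimate open to bias in a known direction. Under an any-time rule, with half to all recurring patients stopping sampling, the null DFS hazard ratio lies between 0.62 and 0.96, depending on stopping and on whether the early end-of-treatment sample counts. It is about 1.0 if nobody stops or if only Week 7 is used. These figures rest on assumed response probabilities, within-patient stability and stopping rates. No size is claimed for OS.

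Confounding by treatment does not depend on the timing rule, because pooling is what the text states. Its size depends on how far response rates differ between arms: 88% against 74% in one illustration, 82% against 79% in the other.

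This is an inexpensive improvement to an exploratory analysis and does not bear on the primary result.

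**What to change.** In Protocol 12.5.2.9 and in the separate immune analysis plan, and for any use of the SAP 5.3 subgroup:

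1. Classify response from samples up to and including Week 13.
2. Start DFS and OS at the Week 13 landmark among patients at risk: alive for OS; alive without recurrence or progression for DFS.
3. Stratify by treatment arm.
4. As an alternative to steps 1 and 2, enter response as a time-dependent covariate in a Cox model stratified by arm.
5. State how CIS patients are handled. Persistence is judged at 6 months and dated back, and clearing patients have a different time origin. A separate or sensitivity analysis would keep Month 6 information from deciding who enters at Week 13.
6. Report an exploratory estimate with a 95% CI, in line with SAP 5.5.

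The cost is analysis wording. In the landmark version, events by Week 13 and responses first seen at Weeks 28 or 56 are not used; the time-dependent version can use later responses.

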## **12.6 Sample Size Estimations**

### **12.6.1 Phase 1**

Phase 1 is designed to provide some indication of safety and tolerability of the low dose of vesigenurtacel-L as a monotherapy. A sample size of 10 patients in the monotherapy setting is deemed suitable for an assessment of safety.

### **12.6.2 Phase 2**

For the randomized portion, a sample size of 75 subjects in the ITT population was selected for this study.

The sample size assessment was based on the following assumptions:

- 75 patients will be randomized to yield 69 evaluable (25 patients per arm)
- A one year disease-free survival rate of 60% in the control and 90% in the respective experimental groups for an absolute difference of 30% in favor of the experimental treatments
- 10% drop-out rate
- Type I error ( $\alpha$ ) = 0.10 and using a one sided test with no adjustment for multiplicity
- Power = 80% to detect a 30% difference in one year disease-free survival between the vesigenurtacel-L groups and the control group
- Patients are followed for three years after the last patient is enrolled

## **13.0 STUDY CONDUCT CONSIDERATIONS**

### **13.1 Regulatory and Ethical Considerations**

Heat Biologics will obtain favorable opinion/approval to conduct the study from the appropriate regulatory agency in accordance with applicable country-specific regulatory requirements or local regulations where applicable prior to a site initiating the study in that country.

The study will be conducted in accordance with all applicable regulatory requirements, including a US IND. The study will also be conducted in accordance with GCP, all applicable patient privacy requirements, and the guiding principles of the Declaration of Helsinki. This includes, but is not limited to, the following:

- IRB/IEC/IBC review and favorable opinion/approval to conduct the study and of any subsequent relevant amending documents
- Patient informed consent
- Investigator reporting requirements

The sponsor will provide full details of the above either verbally, in writing, or both.

Written informed consent will be obtained for each patient before he or she can participate in the study.

### **13.2 Quality Control (Study Monitoring)**

In accordance with applicable regulations, GCP, and Heat Biologics procedures, Heat Biologics monitors, or designee, will contact the site prior to the start of the study to review with the site staff the protocol, study requirements, and their responsibilities to satisfy regulatory, ethical, and Heat Biologics requirements.

Heat Biologics will monitor the study consistent with the demands of the study and site activity to verify that the:

- Data are authentic, accurate and complete.
- Safety and rights of patients are being protected.
- Study is conducted in accordance with the currently approved protocol and any other study agreements, GCP, and all applicable regulatory requirements.
- The investigator agrees to allow the monitor direct access to all relevant documents.

### **13.3 Protocol Deviations**

In general, a protocol deviation is an inadvertent excursion to, or non-compliance with, the IRB approved protocol. The investigator is responsible for ensuring the study is conducted in accordance with the procedures described in this protocol and should not implement any changes to the protocol unless it is required to eliminate an immediate hazard to the patient.

For the purposes of the protocol, deviations that fall into the following categories will be captured on the ECRFs. If the deviation affects the safety of the patient, the sponsor must be notified immediately. Other deviations outside of these categories will be reported to the IRB in accordance with local requirements, as applicable.

- Entered into the study without meeting eligibility criteria
- Developed withdrawal criteria during the study and was not withdrawn
- Received wrong treatment or incorrect dose
- Received excluded concomitant treatment
- Failed to collect data necessary to interpret primary endpoints

### **13.4 Quality Assurance**

To ensure compliance with GCP and all applicable regulatory requirements, Heat Biologics may conduct one or more quality assurance audits. Regulatory agencies may also conduct regulatory inspection of this study. Such audits/inspections can occur at any time during or after completion of the study. If an audit or inspection occurs, the investigator and institution agree to allow the auditor/inspector direct access to all relevant documents and to allocate his/her time and the time of his/her staff to the auditor/inspector to discuss findings and any relevant issues.

### **13.5 Study and Site Closure**

Upon completion or premature discontinuation of the study, the monitor will conduct site closure activities with the investigator or site staff, as appropriate, in accordance with applicable regulations, GCP, and Heat Biologics procedures.

In addition, Heat Biologics reserves the right to temporarily suspend or prematurely discontinue this study at any time for reasons including, but not limited to, safety or ethical issues or severe non-compliance. For this multicenter study, this can occur at one or more sites. If Heat Biologics determines such action is needed, Heat Biologics will discuss this with the investigator, including the reasons for taking such action, at that time. When feasible, Heat Biologics will provide advance notification to the investigator, where applicable, of the impending action prior to it taking effect.

Heat Biologics will promptly inform all other investigators, and/or institutions conducting the study if the study is suspended or prematurely discontinued for safety reasons. Heat Biologics will also promptly inform the regulatory authorities of the suspension or premature discontinuation of the study and the reason(s) for the action. If required by applicable regulations, the investigator must inform the IEC/IRB promptly and provide the reason for the suspension or premature discontinuation.

